# 9. STUDY TREATMENT

# 9.1. Study Drugs Administered

Study drugs are defined as any investigational product or chemotherapy intended to be administered to a study patient according to the study protocol. Study drugs used in this protocol are described in Table 7.

Table 7: Study Drugs

Name	Trilaciclib	Sacituzumab Govitecan-hziy
Type	Investigational Product	Chemotherapy
Dose Formulation	Single-use, sterile powder to be reconstituted and further diluted with 250 mL of normal saline (sodium chloride solution 0.9%) or dextrose 5% in water (D5W) per the Pharmacy Manual	See current prescribing information (Trodelvy Package Insert, 2021)
Unit Dose Strength(s)	300 mg/20 mL	See current prescribing information
Dosage Level(s)	240 mg/m² administered on Day 1 and Day 8 of each 21-day cycle	10 mg/kg reconstituted to a concentration of 1.1 mg/mL to 3.4 mg/mL in normal saline; total volume should not exceed 500 mL administered on Day 1 and Day 8 of each 21-day cycle. Protect from light.
Route of Administration	IV	IV
Infusion Time	30 minutes	3 hours for first infusion; 1 to 2 hours for subsequent infusions if prior infusions were tolerated

IV=intravenous

## 9.1.1. Dose, Dosing Regimen, and Route

Trilaciclib must be administered before sacituzumab govitecan-hziy.

## 9.1.1.1. Trilaciclib – Investigational Product

Trilaciclib for Injection, 300 mg/vial (also referred to as "Trilaciclib Sterile Powder for concentrate for solution for IV infusion, 300 mg/vial") is supplied as a sterile, preservative-free, yellow, lyophilized cake in a single-dose vial (300 mg/20 mL).

Trilaciclib must be reconstituted and further diluted prior to IV infusion as outlined in the Pharmacy Manual. Aseptic technique must be used for reconstitution and dilution. Upon reconstitution, the solution must then be diluted to the calculated dose based on the body surface area (BSA) of the patient. Actual body weight should be utilized for dose calculations. If there is a change in body weight ≥10% relative to the weight at the time of the last dose calculation, dose should be recalculated. Recalculation of dose more frequently per local institutional guidelines is permitted. Dose recalculation to adjust for changes in body weight will not be considered a dose reduction and will be made at the discretion of the

Protocol Amendment 1

G1T28-213

Version 2.0 dated 15 Nov 2021

Investigator. No trilaciclib dose reductions for toxicity management will be allowed during the study.

#### 9.1.1.1.1. Administration of Trilaciclib

- Administer diluted trilaciclib solution as a 30-minute IV infusion no more than 4 hours prior to sacituzumab govitecan-hziy. Do not administer trilaciclib as a bolus.
- Trilaciclib is always administered first. Results from hematology labs should be reviewed prior to administration of trilaciclib. If administration of sacituzumab govitecan-hziy therapy is skipped or discontinued, trilaciclib will also be skipped or discontinued.
- Diluted trilaciclib solution must be administered with an infusion set, including an
  in-line filter (0.2 or 0.22 micron). Compatible in-line filters include polyether
  sulfone (PES), polyvinylidene fluoride, and cellulose acetate.
- Do not administer diluted trilaciclib solution with a polytetrafluorethylene (PTFE) in-line filter. PTFE in-line filters are not compatible with diluted trilaciclib solution.
- Do not co-administer other drugs through the same infusion line.
- Do not co-administer other drugs through a central access device unless the device supports co-administration of incompatible drugs.

If there is any study drug remaining in the infusion bag at the end of the 30 minutes, the infusion should be continued at the same rate until the entire contents of the bag have been administered to ensure patients receive the full dose. Upon completion of infusion of diluted trilaciclib solution, the infusion line/cannula must be flushed with at least 20 mL sterile 5% dextrose (D5W) or 0.9% normal saline.

The infusion rate may be decreased to manage an infusion-related AE; for example, if a patient experiences a burning sensation during infusion, the duration of infusion may be increased to 45 minutes (or longer if clinically indicated) to alleviate the symptoms. The actual start/stop time of infusion will be documented and entered in the eCRF.

## 9.1.1.2. Sacituzumab Govitecan-hziy – Chemotherapy

Descriptions of the formulations of commercially-available sacituzumab govitecan-hziy can be found in the respective current prescribing information. Protocol-specified doses of sacituzumab govitecan-hziy will be administered IV in accordance with institutional guidelines according to the study site's standard practice. Deviation from the recommendations provided in this protocol in order to follow institutional guidelines must receive prior approval from the Medical Monitor or Sponsor.

Actual body weight (not ideal body weight) should be utilized for dose calculations. At a minimum, if there is a change in body weight of >10% relative to the weight at the time of the last dose calculation, doses should be recalculated. Recalculation of the dose more frequently per local institutional guidelines is permitted. Dose recalculation to adjust for changes in body weight will not be considered a dose reduction.

G1T28-213

Prior to each infusion of sacituzumab govitecan-hziy, premedication for the prevention of infusion reactions and CINV is recommended.

- Premedicate with antipyretics, H1 and H2 blockers prior to infusion, and corticosteroids may be used for patients who had prior infusion reactions.
- Premedicate with a two or three drug (preferred) combination regimen (e.g., dexamethasone with either a 5-HT3 receptor antagonist or an NK1 receptor antagonist, as well as other drugs as indicated).

Administer the first infusion over 3 hours and observe patients during the infusion and for at least 30 minutes following the initial dose for signs or symptoms of infusion-related reactions. Subsequent infusions may be administered over 1 to 2 hours if prior infusions were tolerated, and patients should be observed during the infusion and for at least 30 minutes after infusion. Protect infusion bag from light. Do not administer as an IV push or bolus. The actual start/stop time of infusion will be documented and entered in the eCRF.

Trilaciclib is always administered first, followed by sacituzumab govitecan-hziy. Administer diluted trilaciclib solution as a 30-minute IV infusion to be completed within 4 hours prior to the start of sacituzumab govitecan-hziy. If administration of trilaciclib is delayed or discontinued, sacituzumab govitecan-hziy will also be delayed or discontinued. Likewise, if sacituzumab govitecan-hziy is delayed or discontinued, trilaciclib will also be delayed or discontinued.

# 9.1.2. Preparation, Handling, Storage, and Accountability

The Investigator or designee is responsible for study drug accountability, reconciliation, and record maintenance (i.e., receipt, reconciliation, and final disposition records). The Investigator/institution may assign some or all of the Investigator's/institution's duties for investigational product(s) accountability to an appropriate pharmacist or another appropriate individual who is under the supervision of the Investigator/institution.

Further guidance and information are provided in the Pharmacy Manual.

# 9.1.3. Treatment Compliance

The Investigator or designee will dispense the study drugs, via a Pharmacist/Designee, only for use by patients enrolled in the study as described in this protocol. The study drugs are not to be used for reasons other than those described in this protocol. The clinical study site will maintain records of study drugs' receipt, preparation, and dispensing, including the applicable lot numbers; patient's height, body weight, and body surface area; date and time of the start of each trilaciclib and sacituzumab govitecan-hziy infusion; and total drug administered. Any discrepancy between the calculated dose and dose administered and the reason for the discrepancy (e.g., interruption of infusion without restarting) will be recorded on eCRF and in the source documents.

# 9.2. Criteria for Starting Cycle 1 and Each Subsequent Dose

Patients must meet all the following criteria to receive study treatment on Cycle 1 Day 1:

- ANC >  $1.5 \times 10^9$ /L
- Platelet count ≥100 × 10^9/L

- Total bilirubin ≤1.5 × ULN
- AST/ALT  $\leq 3 \times ULN$  or  $\leq 5 \times ULN$  in the presence of liver metastasis
- Other nonhematologic drug-related toxicities must be ≤ Grade 1 (except alopecia or peripheral neuropathy that may be Grade 2 or less).

G1T28-213

Patients must also have ANC  $\ge 1.5 \times 10^9 / L$  to receive any Cycle Day 1 dose of study treatment and ANC  $\ge 1.0 \times 10^9 / L$  to receive any Cycle Day 8 dose of study treatment.

# 9.3. Toxicity Management and Dose Modifications

The dose of trilaciclib will not be modified and will remain at 240 mg/m^2 throughout the study. If administration of sacituzumab govitecan-hziy is discontinued, trilaciclib will also be discontinued.

The dose of sacituzumab govitecan-hziy can be reduced, when necessary, as described below. The recommended dose modification procedures for hematologic and non-hematologic toxicities are described in Table 8. If a subsequent cycle is delayed for toxicity, the patient should still complete the clinical laboratory assessments on the scheduled Day 1 (entered as an Unscheduled assessment in electronic data capture [EDC]) as well as on the actual first dosing day of that cycle. If the delay is secondary to hematologic toxicity, weekly repeat hematology assessments should continue until the finding meets criteria for resumption of dosing.

Treatment with sacituzumab govitecan-hziy will be permanently discontinued for a patient in the event of any Grade 4 infusion reactions which occur after pre-medication with antihistamines, H2 blockers, and steroids.

Recommendation for management of trilaciclib AESIs are provided in Table 9. Recommendations for hepatobiliary toxicity management are in Section 9.3.3.

For dose delays due to toxicity, the patient should be followed (at least) weekly, including CBCs if the AE is hematologic, to monitor the toxicity until treatment criteria are met or until they discontinue treatment. A 3-week delay from the scheduled dose of sacituzumab govitecan-hziy is permitted for toxicity and/or administrative reasons. As examples, if at the scheduled Cycle X Day 1 visit (e.g., Cycle 2 Day 1) a dose delay is needed for toxicity reasons, a delay up to 3 weeks from Cycle X Day 1 for sacituzumab govitecan-hziy is permitted; if at the scheduled Cycle X Day 8 visit (e.g., Cycle 1 Day 8) a dose delay is needed for toxicity reasons, a delay up to 3 weeks from Cycle X Day 1 for sacituzumab govitecan-hziy is permitted. Dosing delays >3 weeks from the scheduled dose of sacituzumab govitecan-hziy may be permitted on a case by-case basis with the documented approval of the Investigator and Medical Monitor.

All recommendations are intended as a minimum guideline for toxicity management and are not a replacement for independent medical judgment tailored to specific circumstances with an individual patient. Please also refer to the individual package insert (Trodelvy Package Insert, 2021) for additional information and recommendations.

Study drug administration will continue until progressive disease per RECIST v1.1 or clinical progression as determined by the Investigator, unacceptable toxicity, withdrawal of consent, Investigator decision, or the end of the study, whichever occurs first.

G1T28-213

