## 7.1. Inclusion Criteria

Patient eligibility should be reviewed and documented by an appropriately qualified member of the Investigator study team before patients are included in the study. Patients must meet *all* of the following inclusion criteria to be eligible for enrollment into the study:

- 1. Age ≥18 years.
- 2. Female or male patient with measurable, unresectable locally advanced or metastatic TNBC.
- 3. Documentation of histologically or cytologically confirmed hormone (estrogen and progesterone) receptor negative tumor by immunohistochemistry (IHC) assessment (defined as <1% nuclei staining) and HER2-negative, non-overexpressing (by IHC [0 or 1+] OR in situ hybridization [ratio <2.0] OR average HER2 gene copy number of <4 signals/nucleus) per 2018 American Society of Clinical Oncology (ASCO) and the College of American Pathologists (ASCO/CAP) criteria. Patients with "estrogen receptor (ER) or progesterone receptor (PR) low positive" as per updated ASCO/CAP 2020 guidelines can be considered after approval by the Medical Monitor.
- 4. Measurable disease as defined by RECIST v1.1.
- 5. Considered to be eligible to receive sacituzumab govitecan-hziy treatment, in the Investigator's judgment.
- 6. Patients must have received 2 or more prior lines of systemic therapy, at least one of them in the metastatic setting.
- 7. Radiation therapy for metastatic disease is permitted as long as the patient has at least 1 measurable lesion that has not been irradiated. Patients should be sufficiently recovered from the effects of radiation as determined by the Investigator but must have completed radiotherapy at least 2 weeks prior to enrollment.
- 8. ECOG performance status of 0 or 1.
- 9. Adequate organ function as demonstrated by the following laboratory values:
  - a. Hemoglobin ≥9.0 g/dL in the absence of RBC transfusion or ESA administration within 7 days prior to the first dose of trilaciclib;
  - b. Absolute neutrophil count (ANC)  $\geq 1.5 \times 10^9$ /L;
  - c. Platelet count  $> 100 \times 10^9 / L$ :
  - d. Estimated glomerular filtration rate >30 mL/minute/1.73 m^2;
  - e. Total bilirubin  $\leq 1.5 \times$  upper limit of normal (ULN);
  - f. ALT and AST  $\leq$ 3 × ULN in the absence of liver metastasis or  $\leq$ 5 × ULN in the presence of liver metastasis.

G1T28-213

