## 9.3.1. Recommended Actions with Sacituzumab Govitecan-hziy for Adverse Events

Recommended dose levels for reduction of sacituzumab govitecan-hziy dose are described below. Sacituzumab govitecan-hziy dose reductions for hematologic toxicities are based on values obtained within 24 hours prior to Day 1 or Day 8 of a given cycle per Investigator discretion and institutional guidelines; recommendations are provided in Table 8. All dose reductions for an individual patient are permanent; and the dose, which has been reduced for toxicity, must not be re-escalated. Up to a maximum of 2 dose reductions will be allowed per patient. If a third dose reduction is required per the modifications below, the patient should discontinue study treatment.

• Starting dose: 10 mg/kg

• First dose reduction: 25% from original dose

Second dose reduction: 50% from original dose

• Third dose reduction: discontinue all study drugs

Note that dose modifications (specifically dose reductions/discontinuations) are recommended for those events considered related to drug (i.e., toxicities) such that decreasing the dose or stopping the drug will lead to improved patient safety. If an event is not thought to be related to study drug by the Investigator, dose reduction/discontinuation is not required since decreasing the dose or stopping the drug would not be expected to alter the risk of the event occurring again; rather, the Investigator should consider if treatment should be delayed until the event recovers to  $\leq$ Grade 1 or baseline before resumption of treatment. Decreased neutrophil, platelet counts or hemoglobin values that occur in isolation (e.g., at nadir) that do not result in a dosing delay, febrile neutropenia, serious adverse event (SAE) or other consequence, do not require dose modification.

If drug-related toxicity requires discontinuation of sacituzumab govitecan-hziy or trilaciclib then the patient must permanently discontinue all study drugs and should complete the Post-Treatment Visit and enter Survival Follow-up.

G1T28-213

Table 8: Recommended Dose Modifications for Sacituzumab Govitecan-hziy

Adverse Event	Occurrence	Dose Modification
Severe Neutropenia		
Grade 4 neutropenia ≥7 days	First	25% dose reduction
OR		and administer
Grade 3 febrile neutropenia (ANC <1000/mm³ and fever		G-CSF
≥38.5°C)	Second	50% dose reduction
OR	Third	Discontinue treatment
At time of scheduled treatment, Grade 3-4 neutropenia		

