which delays dosing by 2 or 3 weeks for recovery to		
≤Grade 1		
At time of scheduled treatment, Grade 3-4 neutropenia	First	Discontinue treatment
which delays dosing beyond 3 weeks for recovery to		
≤Grade 1		
Severe Non-Neutropenic Toxicity		
Grade 4 non-hematologic toxicity of any duration	First	25% dose reduction
OR	Second	50% dose reduction
Any Grade 3-4 nausea, vomiting, or diarrhea due to	Third	Discontinue treatment
treatment that is not controlled with antiemetics and		
anti-diarrheal agents		
OR		
Grade 3-4 non-hematologic toxicity persisting >48 hours		
despite optimal medical management		
OR		
At time of scheduled treatment, Grade 3-4 non-neutropenic		
hematologic or non-hematologic toxicity, which delays		
dose by 2 or 3 weeks for recovery to ≤Grade 1		
In the event of Grade 3-4 non-neutropenic hematologic or	First	Discontinue treatment
non-hematologic toxicity, which does not recover to		
≤Grade 1 within 3 weeks		

ANC=absolute neutrophil count; G-CSF=granulocyte colony-stimulating factor

Source: Table recreated from Trodelvy Package Insert, 2021

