#### 11. STUDY ASSESSMENTS

Study procedures and their timing are summarized in the Schedule of Assessments (Table 6). Adherence to the study design requirements, including those specified in the Schedule of Assessments, is essential and required for study conduct. Immediate safety concerns should be discussed with the study Medical Monitor upon occurrence or awareness to determine if the patient should continue or discontinue study intervention.

The Investigator or Designee will maintain a screening log to record details of all patients screened and to confirm eligibility or record reasons for screening failure, as applicable.

Procedures conducted as part of the patient's routine clinical management (e.g., hematology, chemistry) and obtained before signing of the informed consent form (ICF) may be utilized for screening or baseline purposes provided the procedures met the protocol-specified criteria and are performed within the permitted 30-day Screening period.

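### The mandatory stop of sacituzumab govitecan after a Grade 4 infusion reaction depends on three premedications the protocol does not require; without all three, the only rule specific to that drug is a 25% dose reduction

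*Protocol*

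**What the plan says.** **The stop rule.** Protocol Section 9.3 says SG will be permanently discontinued for "any Grade 4 infusion reactions which occur after pre-medication with antihistamines, H2 blockers, and steroids". The three drug classes are joined by *and*. No sentence covers a Grade 4 infusion reaction when one of them was not given.

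**Premedication.** Section 9.1.1.2 says "premedication for the prevention of infusion reactions and CINV is recommended". Antipyretics and H1 and H2 blockers are listed for infusion reactions. Steroids for that purpose are optional: "corticosteroids may be used for patients who had prior infusion reactions". The recommended antiemetic regimen has two or three drugs and gives as its example "dexamethasone with either a 5-HT3 receptor antagonist or an NK1 receptor antagonist".

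**SG dose rules.** Table 8 in Section 9.3.1 has no row for infusion reactions. Its row for "Grade 4 non-hematologic toxicity of any duration" prescribes a 25% reduction at the first occurrence, 50% at the second and discontinuation at the third. The accompanying list says "First dose reduction: 25% from original dose", from a starting dose of 10 mg/kg.

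**Trilaciclib rules.** Table 9 and Section 4.3.3.1 call for permanent discontinuation of trilaciclib after Grade 3 or 4 acute drug hypersensitivity. Premedication is not a condition. Section 9.1.1.2 stops SG when trilaciclib is stopped. Section 9.3.1 stops all study drugs when drug-related toxicity requires either to be discontinued.

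**The concern.** Section 17.2.3 defines Grade 4 as life-threatening, and Section 4.3.3.2 lists severe anaphylactic reactions among the important SG risks. After such an event an investigator should find one clear instruction. Here the stop depends on what was given before the infusion, and the protocol does not require what the stop depends on. A patient can be treated fully in line with the protocol and still have a Grade 4 reaction that the mandatory stop does not reach. The table consulted next then gives a reduced dose. What is at stake is possible re-exposure of an individual patient to a drug that has just caused a life-threatening reaction, with the decision to stop resting on judgment and on which drug is blamed.

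**Working it through.** This is a check of wording. The only arithmetic is the dose.

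**Step 1. Can a protocol-compliant patient fall outside the Section 9.3 condition?** Yes.
- Premedication as a whole is a recommendation.
- Steroids against infusion reactions are optional and tied to a prior reaction. That prior reaction need not have been to SG. Inclusion criterion 6 says "Patients must have received 2 or more prior lines of systemic therapy", so some patients may bring such a history. Patients with no such history are not directed to a steroid for this purpose, including at the first SG infusion.
- Antiemetic dexamethasone is an example, not a requirement. The protocol does not say whether it counts as the steroid in Section 9.3. If it does, many patients will meet the condition.

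**Step 2. Which SG rule then applies to a drug-related Grade 4 reaction?**
- The Table 8 row for "Grade 4 non-hematologic toxicity of any duration" fits. First reduction: 10 mg/kg × (1 − 0.25) = 7.5 mg/kg. Second: 10 mg/kg × (1 − 0.50) = 5 mg/kg. The third occurrence ends treatment.
- The Table 8 row that stops treatment at first occurrence for non-neutropenic toxicity needs failure to recover to Grade 1 or less within 3 weeks. A reaction that resolves sooner does not meet it.

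**Step 3. Does Section 10.1 make a stop binding?** One criterion there applies where the toxicity rules in Section 9.3 indicate permanent discontinuation. For this reaction the SG rules do not, so that link is not triggered by them.

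**Step 4. Do the trilaciclib rules reach the event?** It depends on how the event is classified.

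| Handling of the Grade 4 reaction | Rule | Result for SG |
|---|---|---|
| All three premedications given | Section 9.3 | Permanent stop |
| Not all three; handled as trilaciclib acute hypersensitivity | Table 9, carried to SG by Sections 9.1.1.2, 9.3.1 and 10.1 | Stop, in conflict with Table 8 |
| Not all three; attributed to SG alone and not handled as a trilaciclib event | Table 8 | 7.5 mg/kg, unless stopped on judgment |

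Section 9.3.2 presents Table 9 as suggested actions for trilaciclib, so whether it governs a reaction during the SG infusion is unclear. The gap is the last row; the second row is a conflict between two tables.

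**Step 5. How many patients?** The documents give neither a Grade 4 infusion-reaction rate for SG nor the share of patients treated without all three classes. Any probability would be a product of two assumed inputs, so none is given. SAP Section 1.1 reports that enrollment closed on 14 February 2023 with 30 patients, so a change now helps only those still receiving SG.

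**The case against.** The strongest reply is that the rest of the protocol already handles this event.

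- **Table 9.** Trilaciclib is completed within 4 hours before SG on the same day, so blaming SG alone will often be difficult. SAP Appendix 2 places infusion-related reaction under the injection-site category of trilaciclib adverse events of special interest, and anaphylactic reaction and shock under acute hypersensitivity. Table 9 stops trilaciclib for Grade 3 or 4 events in both categories. This stands in part, and it rules out a stronger reading that a reader might infer, namely that Table 8 is the only rule for every such reaction. It does not settle the matter. The Appendix 2 lists are reporting queries, not bedside instructions, and Table 9 is written for trilaciclib.
- **Usual care.** A patient given H1 and H2 blockers plus dexamethasone has had all three classes on an ordinary reading. This also stands: a reader should not infer that most patients fall outside the stop. It leaves those given a steroid-free antiemetic regimen or incomplete premedication.
- **Judgment.** A reader might infer that the protocol compels re-treatment. It does not. Section 9.3 calls its recommendations a minimum guideline, preserves medical judgment and ends treatment for unacceptable toxicity. Section 10.1 stops study drugs for an event judged an unacceptable risk. Section 11 adds: "Immediate safety concerns should be discussed with the study Medical Monitor upon occurrence or awareness to determine if the patient should continue or discontinue". These routes soften the gap, but they leave the Table 8 instruction in place and make stopping discretionary.
- **Package insert.** Section 9.3 refers to it and Table 8 is sourced from it. It was not available, so whether it closes the gap is unknown.

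**Conclusion.** The point holds as a minor patient-safety improvement. The mandatory SG stop is conditional on three premedications that the protocol does not require, and the only SG-specific dose rule left for a first Grade 4 reaction outside that condition is a reduction to 7.5 mg/kg. Because Table 9 can lead to a stop of both drugs, the defect is confined mainly to reactions attributed to SG alone; where Table 9 is applied, it conflicts with Table 8. The affected group is probably small.

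The conclusion assumes that the reaction is considered drug-related, since Section 9.3.1 ties dose modification to related events, and that the package insert does not add an unconditional stop. Nothing here bears on PFS, power or the SAP.

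**What to change.** 1. In Section 9.3, replace the conditional sentence with: *Sacituzumab govitecan-hziy and trilaciclib will be permanently discontinued for any Grade 4 infusion reaction, whether or not premedication was given.*
2. In Table 8, add the row: *Grade 4 infusion reaction; First; Discontinue treatment (see Section 9.3).*
3. In Table 8, extend "Grade 4 non-hematologic toxicity of any duration" with the words *other than infusion reaction*.

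This follows the protocol's own rule for trilaciclib hypersensitivity. It also removes the question whether antiemetic dexamethasone counts as the steroid, and the dependence on which drug is blamed.

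The cost is a clarification letter or short amendment, with no change to data collection or the SAP. The clinical downside is that premedicated rechallenge after a Grade 4 infusion reaction would no longer be allowed.
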